## 7.3.1 Experimental Sessions

## 7.3.1.1 Psychotherapy Session

There will be two open-label Experimental Sessions (Visits 5 and 10). Procedures for MDMA-assisted psychotherapy will remain the same across all sessions and all procedures regardless of dose received (Table 7). Experimental Sessions must be at least 8 hours long, measured from 30 minutes prior to IP administration.

- Experimental Session 1 (Visit 5) will occur within 1 week of the Baseline CAPS-5 (Visit 3) assessment. If the Baseline CAPS-5 assessment is completed outside of the allowed window, the investigator should consult the CRA and Medical Monitor to determine if the assessment should be repeated. The first Experimental Session will include 80 mg of IP followed by a supplemental half-dose 1.5 to 2 hours after the initial dose unless tolerability issues emerge with the first dose or the participant declines.
- Experimental Session 2 (Visit 10) will occur within 3 to 5 weeks of Experimental Session 1 (Visit 5) and after Integrative Session 1.3 (Visit 9). A dose of 80 or 120 mg MDMA will be administered. A supplemental half-dose will be administered 1.5 to 2 hours after the initial dose unless tolerability issues emerge with the first dose or the participant declines.

Table 8: Schedule of Procedures for Experimental Sessio
--

Approximate Time	Procedure or Action
9:30	Urine drug screen, alcohol test (UK only), pregnancy test, Symptom-
	directed Physical Exam, concomitant medication information collected,
	participant acclimated to environment, C-SSRS
9:55	Baseline BP, body temperature, pulse, SE
10:00	IP Administration, Begin video recording
11:30	BP, body temperature pulse, SE
	Supplemental Dose Administration, unless tolerability issues emerge
	with the first dose or the participant declines
17:30	C-SSRS, BP, body temperature, pulse, SE

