1.0 Definitions of Terms

Categorical data: refers to discrete (indivisible) variables, such as gender or ethnicity; data will be presented as total numbers of each category as needed to describe the sample

Completers: are defined as participants who complete all two planned experimental sessions and the CAPS-5 outcome assessment 14 weeks after enrollment (Visit 14).

Descriptive data: includes mean, median, standard deviation, minimum, and maximum of numerical data used as needed to describe the sample

Difference scores: consist of scores computed by subtracting one value from another, as subtracting Baseline from follow-up score, used to test for differences between and within groups to determine change as a function of experimental treatment over time

Dropouts: are defined as participants who withdraw consent due to any reason after dosing and no longer participate in the study, i.e. no further contact with investigators or site staff.

Effectiveness: type of analysis used to assess therapeutic effects or benefits

Exploratory analyses: inferential or descriptive analysis of the data to determine trends that might lead to hypotheses for further study

Frequency listing: tabular listing of numbers and/or percentages of events used as needed to describe the sample or data characteristics

Outcome measures: primary and secondary study measures that are used to test the study hypotheses

Post-dosing Early Terminators: are defined as participants who discontinue study treatment but continue to participate in study evaluations and outcome assessments.

Pre-dosing Early Terminators: are defined as participants who discontinue participation after enrollment but before randomization during the Preparatory Period and never receive study drug.

Process measures: study measures or qualitative observations collected during the study that may increase depth of understanding of the condition and treatment, although not necessarily related to safety or effectiveness

Protocol deviation: event that represents significant divergence from the intended study design as described in the protocol

Safety: assessment of indicators of potential risks and adverse events

Safety measures: study measures that assess safety of the Investigational Product (IP), such as heart rate monitoring, blood pressure, body temperature

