3.3 Safety Objectives

The overall safety objective is to assess severity, incidence and frequency of AEs, AEs of Special Interest (AESIs), and Serious Adverse Events (SAEs), concomitant medication use, suicidal ideation and behavior, and vital signs to support the package insert for MDMA-assisted psychotherapy. The following safety objectives will evaluate the safety of MDMA-assisted psychotherapy:

- 1. Assess incidence of AEs during Experimental Sessions that may be indicative of a medical complication of the Investigational Product (IP), such as clinical signs and symptoms of chest pain, shortness of breath, or neurological symptoms or any other signs or symptoms that prompt additional vital sign measurements.
- 2. Assess incidence of AEs by severity.
- 3. Assess incidence of Treatment Emergent AEs (TEAEs) by severity.
- 4. Assess incidence of TEAEs by severity taken during an Experimental Session and through 2 days after IP administration.
- 5. Assess incidence of AESIs, defined as AEs specified in he protocol related to cardiac function and abuse liability.
- 6. Assess incidence of AEs by severity categorized as leading to discontinuation of IP, resulting in death or hospitalization, and continuing at Study Termination.
- 7. Assess incidence of SAEs.
- 8. Assessincidence of psychiatric concomitant medications taken during an Experimental Session and through 2 days after IP administration.
- 9. Assess incidence of any psychiatric concomitant medications taken during the Treatment Period.
- 10. Assess incidence of serious suicidal ideation and positive suicidal behavior assessed with the Columbia Suicide Severity Rating Scale (C-SSRS).
- 11. Assess mean changes in blood pressure, heart rate, and body temperature from pre-IP administration to end of each Experimental Session.

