8.8.2 Analysis of Adverse Events

The primary measure of safety will be the reporting of unsolicited AEs. All AEs collected from Enrollment to Termination will be categorized as follows:

- Pretreatment AEs are defined as AEs that occur during the Preparatory Period prior to the first dose in the first Experimental Session
- Treatment Emergent AEs are defined as AEs that occur during the Treatment Period from the first Experimental Session to the last Integrative Session
- AEs that occur on and two days after MDMA or placebo administration
- AESIs are defined as AEs specified in the protocol related to cardiac function and abuse liability
- Follow-up Period AEs are defined as AEs that occur during the Follow-up Period after the last Integrative Session through Termination
- AEs leading to discontinuation of IP
- AEs resulting in death or hospitalization.
- SAEs
- AEs continuing at Termination.

Verbatim terms on case report forms will be mapped to preferred terms (PT) and system organ class (SOC) using the Medical Dictionary for Regulatory Activities (MedDRA) Version 20.0 (Hierarchy), WHO DRUG Enhanced Mar-2018 B3 (Hierarchy and Ingredients).

Frequency and incidence of AEs will be displayed by PT, sorted by SOC, and summarized by treatment group, analysis set, category (as defined above), severity, and seriousness. AEs will be analyzed and presented as follows:

- If a participant has more than one AE mapped to the same PT, that AE will be reported once using the highest severity
- Relationship will be determined based on relative incidence of TEAEs with at least twofold difference between MDMA vs. placebo
- Compare relative incidence of AEs during Experimental Sessions such as clinical signs and symptoms, such as chest pain, shortness of breath, or neurological symptoms or any other signs or symptoms that may be indicative of a medical complication of the investigational product
- AEs that occur on day of Experimental Sessions and two days after IP administration will be presented separately.

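### SAP 8.8.2 asks for AE frequency and incidence, but its once-per-PT rule is not limited to incidence; if frequency means events, a reaction at both MDMA sessions is counted once

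*SAP*

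**What the plan says.** The overall safety objective in SAP 3.3 is to "assess severity, incidence and frequency of AEs", so incidence and frequency are named as separate quantities. SAP 8.8.2 carries both into the tables: "Frequency and incidence of AEs will be displayed by PT, sorted by SOC". It then lists how AEs will be analysed and presented, and the first item is the counting rule: "If a participant has more than one AE mapped to the same PT, that AE will be reported once using the highest severity". Nothing confines that rule to incidence.

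Three other SAP statements bear on the reading:

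- SAP 1.0 describes a frequency listing as a "tabular listing of numbers and/or percentages of events used as needed to describe the sample or data characteristics".
- The treatment-emergent category spans both dosing sessions: "Treatment Emergent AEs are defined as AEs that occur during the Treatment Period from the first Experimental Session to the last Integrative Session".
- Session-related events get their own display: "AEs that occur on day of Experimental Sessions and two days after IP administration will be presented separately". It is not said to be split between Session 1 and Session 2.

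Protocol 13.1.2 states the same once-per-PT rule, also without a limit. Its AE text asks for incidence and does not mention AE frequency.

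**The concern.** Incidence counts participants with at least one event. Frequency, read as a count of events, should also reflect repeats. Collapsing all records of one preferred term in one participant to a single record is correct for incidence. Applied to an event count, it makes the frequency of each preferred term equal to the number of participants with it, so the frequency display adds nothing.

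The design makes repeats plausible. Participants are planned for two open-label MDMA sessions (Protocol 7.3.1.1), and Protocol 9.2.4.1 describes the common reactions as transient and typically seen during sessions. The same term can therefore start, resolve and return. Both sessions fall in one treatment-emergent category, so summarising by category does not separate them. By contrast, SAP 8.8.4 and 8.8.5 tabulate suicidality and vital signs for each Experimental Session.

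AE reporting is the primary safety measure in SAP 8.8.2, and the safety objective says the data are to support a package insert. How often a reaction occurs across repeat dosing is part of that description.

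**Working it through.** The documents state no AE rate, event count or sample-size figure that bears on this, so there is no plan figure to reproduce. The check is a reading of the text followed by simple counting under stated assumptions.

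**Text**

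1. The sentence directly before the rule covers frequency and incidence together.
2. The rule that follows has no qualifier.
3. No other rule in either document produces an event count.
4. Followed literally, events per preferred term therefore equal participants per preferred term within a category, and both sessions are in the same category.

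**Counting**

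Inputs from the documents:
- two sessions, Visits 5 and 10 (Protocol 7.3.1.1);
- up to 40 participants (Protocol 4.1). N = 40 with everyone completing both sessions is an upper-end illustration.

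Assumptions:
- at most one event of a given term per participant per session;
- the same probability p at each session;
- c = probability of the event at Session 2 given the event at Session 1.

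Formulas:
- True events = 2pN
- Count under the once-per-PT rule = (2p − pc)N
- Shortfall = pc / 2p = c/2, whatever p is

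Results for N = 40:

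| p | c | True events | Counted once per PT | Shortfall |
|---|---|---|---|---|
| 0.10 | 0.10 | 8 | 7.6 | 5% |
| 0.25 | 0.25 | 20 | 17.5 | 12.5% |
| 0.50 | 0 | 40 | 40 | 0% |
| 0.50 | 0.50 | 40 | 30 | 25% |
| 0.50 | 0.75 | 40 | 25 | 37.5% |
| 0.50 | 1 | 40 | 20 | 50% |

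Example: p = 0.50, c = 0.75 gives 2 × 0.50 × 40 = 40 events and (1.00 − 0.375) × 40 = 25 counted, so 15 of 40 (37.5%) are missing. Rows with c = p are the case where the two sessions are independent, and the shortfall is then p/2. For one participant with the term at both sessions, two events give one count. The shortfall can exceed 50% only if a term also recurs within a session window, which these assumptions exclude.

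**The case against.** The best counter-argument is that frequency here means the number of participants, shown beside a percentage. SAP 8.0 describes nominal variables by frequencies and percentages, and SAP 8.8.1 uses the same pair for participants with exposure. On that reading the once-per-PT rule is the ordinary convention and nothing is under-counted. The reading is possible, so the under-count is conditional. It is not the better fit: SAP 1.0 ties a frequency listing to events, SAP 8.8.1 says participants when it means participants, and the objective would otherwise name one quantity twice. SAP 1.0 defines a listing rather than the 8.8.2 tables, so it is supporting evidence and not proof. Either way, two programmers could build different tables from the present text.

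Other limits also stand:

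- The numbered AE objectives in SAP 3.3 (items 1 to 7) ask only for incidence, which the rule estimates correctly. Frequency appears only in the overall objective and in 8.8.2.
- Protocol 9.2.4.1 ties common reactions to sessions. It does not say that the same participant has the same reaction at both, so recurrence is an inference.
- SAP 8.0 provides data listings, where individual recurrences may be seen. No record is lost, and no test or decision rule uses an event count.

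Two stronger readings are tempting and are not supported. A reader might infer that the rule raises a mild recurrence to the grade of the worst episode. It does not: the term is reported once, so the mild episode is left out. A reader might also infer that Protocol 13.1.2 is itself in conflict because it repeats the rule. Its AE text asks only for incidence, and it pairs frequency with incidence only for concomitant medications and suicidality. The conflict is within the SAP.

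**Conclusion.** The point holds in conditional form. SAP 8.8.2 promises two quantities and gives a rule that suits only one of them. If frequency means events, which is the more natural reading of the SAP's own terms, the summary tables under-count any preferred term that recurs at the second session. The shortfall is c/2, between 0% and 50%, given at most one event of a term per session and equal per-session probability. The documents give no basis for choosing a value in that range, and it is zero for a term that never recurs. Participant-level incidence is correct as planned. This is a reporting gap in the summary tables that should be closed before they are programmed; it does not invalidate the safety analysis.

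**What to change.** In SAP 8.8.2, replace the once-per-PT item with: *For incidence, a participant with more than one AE of the same PT is counted once at the highest severity; for frequency, every AE record is counted at its own severity.* Show both columns in the AE tables: number of participants (%) and number of events. Reword the once-per-PT sentence in Protocol 13.1.2 to match, as the rule for incidence.

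The cost is one sentence and a slightly wider table. The AE records are already collected from Enrollment through Study Termination (Protocol 10.1), so no new data or visits are needed, and the incidence figures do not change.

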## 10.0 Safety

### 10.1 Adverse Events

An Adverse Event (AE) is defined as any medical occurrence in a participant, including any abnormal sign (*e.g.*, abnormal physical exam or laboratory finding), symptom, or disease, temporally associated with the participant's involvement in the research, whether or not considered related to participation in the research. This definition includes concurrent illnesses or injuries and exacerbation of pre-existing conditions.

Events related to planned treatments or physician visits for Baseline conditions collected in the medical history will not be collected, unless there is an exacerbation of the condition, in which case they will be actively followed until resolution.

An unexpected AE is one that is not listed in the current IB or an event that is by nature more specific or more severe than a listed event.

The site physician will be responsible for reviewing and confirming all AEs and SAEs collected during the study. The therapy teams will collect AEs during study visits from Enrollment (Visit 0) through Study Termination (Visit 15). All SAEs will be collected from the time of informed consent signed through Study Termination (Visit 15). Participants will be asked directly how they are feeling during each contact, and AEs may be captured spontaneously during psychotherapy sessions, telephone calls, or other correspondence. Completed measures may create suspicion that an AE occurred; in this case, the site staff should follow-up with the participant.

All AEs will be monitored by the therapy team until resolution or, if the AE becomes chronic, a cause can be identified. If an AE is unresolved when a participant terminates from the study, a clinical assessment will be made by the site physician, investigator, and/or Medical Monitor as to whether continued follow-up of the AE is warranted.

The severity of events reported on the "Adverse Events" eCRF will be determined by the site physician as:

- Mild: No limitation in normal daily activity
- Moderate: Some limitation in normal daily activity
- Severe: Unable to perform normal daily activity

The seriousness and relationship of study treatment to an AE will be determined by the Investigator based on the following definitions:

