- 1. "Not Related": The AE is not related if exposure to the investigational product has not occurred, or the occurrence of the AE is not reasonably related in time, or the AE is considered unlikely to be related to use of the investigational product, *i.e.*, there are no facts (evidence) or arguments to suggest a causal relationship, or the AE is more likely related to the subject's pre-existing condition.
- 2. "Related": The administration of the investigational product and AE are considered reasonably related in time and the investigational product is more likely than other causes to be responsible for the AE or is the most likely cause of the AE.

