All SAEs will be collected from the time of informed consent through Study Termination. All SAEs which occur during the course of the trial, whether considered to be associated with IP or not, must be reported to the sponsor within 24 hours of the site staff's awareness of occurrence. Reporting procedures will be provided to the site. All SAEs will be assessed for relationship, expectedness and any required actions to address safety at the time of reporting of the event. SAEs will be evaluated by the site physician and Medical Monitor to determine if it is appropriate for the participant to continue treatment or enter follow-up. Any participant who experiences a SAE considered related to the IMP administration will be permanently discontinued from future IMP treatments. All SAE's must be reported by the investigator to his/her corresponding EC or applicable regulatory authorities in accordance with institutional policy/regulatory requirements and adequate documentation of this notification must be provided to the Sponsor.

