6.0 Randomization and Blinding

MP18 is an open-label study with no randomization or blinding of treatment.

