7.0 Sample Size and Power Considerations

MP18 is a one-arm interventional study. Thus, no power nor sample size calculations were required.

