8.0 Analyses

Every effort will be made to ensure complete, accurate and timely data collection and to avoid missing data, to ensure the completeness of the data which can impact the integrity and accuracy of the final study analysis. The statistical analyses will be reported using summary tables, figures, and data listings. All analyses and tabulations will be performed using SAS® Version 9.4 or higher, and S-PLUS. In general, nominal variables will be described in terms of frequencies and percentages. Ordinal and non-normal continuous variables will be described using sample median and range.

Approximately normal variables will be described using sample mean and standard deviations and analyzed by parametric statistical tests. Except for the primary effectiveness analysis, all statistical tests will be two-sided and a difference resulting in a p-value of less than or equal to 0.05 will be considered statistically significant. All p-values will be rounded to and displayed in four decimals. If a p-value less than 0.0001 occurs it will be shown in tables as <0.0001. Data not subject to analysis according to this plan will not appear in any tables or graphs, but will be included in the data listings. Selected results may be presented graphically using standard graphical software.

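### SAP 8.8.2 decides adverse event relationship by comparing MDMA with placebo, but MP18 has one open-label arm and no placebo, so the rule classifies nothing and contradicts Protocol 10.1

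*SAP*

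**What the plan says.** SAP 8.8.2, in its list of how adverse events will be analysed and presented, gives this rule: "Relationship will be determined based on relative incidence of TEAEs with at least twofold difference between MDMA vs. placebo".

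The same SAP describes the design in two places. Section 6.0 says "MP18 is an open-label study with no randomization or blinding of treatment", and section 7.0 says "MP18 is a one-arm interventional study".

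Protocol 10.1 assigns relationship differently: "The seriousness and relationship of study treatment to an AE will be determined by the Investigator based on the following definitions". Two definitions follow, Not Related and Related. The second requires a reasonable relation in time and that "the investigational product is more likely than other causes to be responsible for the AE", or that the product is the most likely cause.

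For tables, SAP 8.8.2 says that adverse events are "summarized by treatment group, analysis set, category (as defined above), severity, and seriousness". SAP 8.0 adds a default: data that the plan does not analyse "will not appear in any tables or graphs, but will be included in the data listings".

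**The concern.** A rule that compares MDMA with placebo needs placebo participants, and this trial has none. If the rule cannot run and no other line of the plan tabulates relationship, the SAP yields no relationship result in any table or graph. The analyst must then choose, with the adverse event data already in hand, whether to drop the rule, borrow a placebo rate from another study, or use the Investigator's assessments. The SAP treats adverse event reporting as its primary measure of safety, so that choice should be made beforehand.

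The rule also gives relationship a meaning that the protocol does not. A reader of the study report could not tell which of the two was intended.

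**Working it through.** The plan gives no figure to reproduce here. The check is of denominators and counts.

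**1. Can the rule be applied?**

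Inputs:
- Number of arms: 1 (SAP 7.0).
- Planned participants: up to 40 (Protocol 4.1), all scheduled for MDMA at two open-label sessions (Protocol 7.3.1.1; SAP 5.0, Table 1).
- Placebo participants: 0.

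Reading the twofold difference as a ratio, the rule requires for each preferred term *t*:

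(x_MDMA,t / n_MDMA) ÷ (x_placebo,t / n_placebo) ≥ 2

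With n_placebo = 0 and hence x_placebo,t = 0, the second bracket is 0/0. The ratio is undefined for any MDMA count from 0 to 40. Reading the rule as some other form of difference does not help, because the placebo incidence is still missing. Events classified: 0.

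**2. Does either document supply an outside placebo rate?**

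- SAP 2.0 names MP16 and MP17 as sister studies. Both are open-label.
- Protocol 1.2.4, 9.2.3.1 and 9.2.4.1 mention placebo-controlled work by the sponsor, but give no placebo event rates by term.
- Neither document ties any of that work to the rule.

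**3. How does the rule compare with Protocol 10.1?**

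| | Protocol 10.1 | SAP 8.8.2 |
|---|---|---|
| Who or what decides | The Investigator | A computed ratio |
| Unit | The single event | Incidence across participants |
| Criterion | Timing and likely cause | At least twofold against placebo |

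The two differ on all three points.

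**4. Does anything else in the plan tabulate relationship?**

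- Summary dimensions in SAP 8.8.2: treatment group, analysis set, category, severity, seriousness. Relationship is in 0 of 5.
- Event categories in SAP 8.8.2: pretreatment; treatment-emergent; day of dosing and two days after; special interest; follow-up; leading to discontinuation; death or hospitalization; serious; continuing at termination. Relationship is in 0 of 9.
- Protocol 13.1.2 adds no table by relationship.
- Safety objectives in SAP 3.3: 0 of 11 ask for one.

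With no table assigned, the SAP 8.0 default sends the Investigator's assessments to the listings. This is an inference from the two sections together; no sentence says it outright.

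**The case against.** The strongest reply is that the rule does no harm. It has no denominator, so it cannot misclassify an event, bias an estimate or overwrite an Investigator's assessment. No safety objective and no part of Protocol 13.1.2 promises a table by relationship, so no promised result is lost. Serious events are covered separately: "All SAEs will be assessed for relationship, expectedness and any required actions to address safety at the time of reporting". Other controlled-trial wording recurs in the SAP, such as references to randomized participants and a blinded session in section 8.1, so this looks like a matter for editing. All of this is correct, and it limits the size of the point. It does not remove it: the other leftovers are mostly descriptive, whereas this bullet prescribes an analysis and is the only rule the SAP gives for relationship.

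A second reply is that the SAP may intend a screen at the level of the term, separate from the Investigator's judgment of single events. The SAP does not say so, and that reading needs a placebo rate just as much.

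A third reply is that the listings default may not apply, because relationship is named in a list of planned analyses. But the analysis named there cannot be run, so no planned table results. A related caution does stand. Protocol 10.1 mentions the eCRF expressly for severity only, so the presence of the Investigator's assessments in the listings depends on that field having been captured.

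**Conclusion.** The concern holds. As written, the SAP's only rule for relationship can classify 0 events, and it conflicts with Protocol 10.1 on assessor, unit and criterion. Relationship would reach no table or graph and would appear in listings only.

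The consequence is limited to one safety presentation. Effectiveness analyses, data collection and the handling of serious events are unaffected. It should be corrected before the analysis.

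The conclusion rests on two assumptions: that no outside placebo data are meant, since none are named, and that the SAP 8.0 default governs data with no assigned table.

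**What to change.** Replace the bullet with wording such as: *Relationship is as assessed by the Investigator under Protocol 10.1; treatment-emergent adverse events are tabulated overall by this assessment.* Confirm first that the relationship field is in the database.

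The minimum cure is to delete the rule and defer to Protocol 10.1. The table goes one step further than any safety objective requires, but it turns a rule with no output into a usable summary, and SAP 8.8 already provides for overall tabulation.

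Three clerical edits can be made in SAP 8.8.2 at the same time:
- Remove the mention of placebo from the category for the day of dosing and two days after.
- Remove treatment group from the summary dimensions, since a one-arm study has only one.
- The bullet that compares relative incidence of events during sessions names no comparator. Either align it with Protocol 13.1.2, which asks only that incidence be reported, or state the within-arm comparison meant (by session or by initial dose).

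The cost is SAP wording and one additional table. Provided the field exists, data collection, endpoints and serious event reporting do not change.
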